AV006	Children (15-71 months old)	Vaccine efficacy =93% (95% CI =88-96% against culture-confirmed influenza pneumonia; 98% efficacy against influenza associated otitis media
AV006	Children	Vaccine efficacy=87% (95% CI=78,93) against culture-

(second year)	(15-71 months old)	confirmed influenza following the first annual influenza revaccination.; 94% efficacy against influenza-associated otitis media
AV011	Children	Reduction in viral shedding of vaccine virus after intranasal challenge (efficacy=83%; 95% CI=60,93)
AV003	Adults	Vaccine efficacy = 85% (95% CI=28,100) against laboratory-confirmed influenza
AV009	Adults	19% (95% CI=7-29) reduction of severe febrile illnesses; 24% (95% CI=13,33) reduction in febrile upper respiratory illness; Reduction also seen for days of work lost, of health care provider Visits, use of prescription antibiotics, and use of over the Counter medication during the peak influenza period.

The ease of administration of CAIV-T by intranasal sprayer could lead to increased compliance and better public health control of influenza and therefore, a reduction in the impact of this disease.

As with any vaccine, CAIV-T may not protect 100% of individuals given the vaccine. The following are additional risks that may be associated with CAIV-T.

CAIV-T was generally well tolerated in clinical trials. In children in the 10 days following Dose One, the most common events were fever (5% over placebo), runny nose/nasal congestion (11% over placebo), and vomiting, muscle aches, headaches and decreased activity (each approximately 2% over placebo). However, following Dose Two and after annual re-vaccination, there were no significant differences between the vaccine and placebo group.

Currently, there have been no serious adverse experiences attributed to CAIV-T in completed clinical trials performed by Aviron, Inc. or Wyeth Lederle Vaccines. CAIV-T is contraindicated in individuals hypersensitive to any component of the vaccine. Intranasal influenza virus vaccine is propagated in eggs. Therefore, CAIV-T should not be administered to anyone with a history of hypersensitivity to eggs. The occurrence of a hypersensitivity reaction to the vaccine following vaccination with CAIV-T is a contraindication to further use of this product.

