The data in Table 2 represent the cumulative total of subjects who experienced at least one episode of the symptom, irrespective of severity, during the 11 days of follow-up post-vaccination (Study Day 0 to Study Day 10) as obtained from worksheets completed by the parents or legal guardians. These are parental or legal guardian observations and did not involve pre-defined symptomatology.

No clinically pertinent differences can be observed between the rates of reactogenicity episodes in D153P500 for either study group and for either dose of the frozen or liquid formulations. The rates of respiratory symptoms following each dose were consistent between the two groups in D153P500, and importantly were also consistent with data summarised from Aviron clinical trials where approximately one-third of children aged 12 to 23 months experienced cough and 69% experienced runny nose or nasal congestion following receipt of CAIV-T 37; and in previously published observations in the 2 month old to 18 month old age group, where at least one-third experienced cough and 57% experienced runny nose or nasal congestion following receipt of bivalent influenza A CAIV, compared with a rate of 50% in placebo recipients 39.

Table 2
Study D153P500 Reactogenicity events with onset Day 0 to 10 by Dose and Treatment Group (All data blinded)—Children 12-36 months of age

Events	Post-dose 1		Post-dose 2	
	Group 1 (n=662)	Group 2 (n =658)	Group 1 (n=649)	Group 2 (n=649)
Cough	341 (52)	313 (49)	289 (45)	265 (42)
Runny nose/	478 (73)	445 (69)	371 (58)	363 (57)
Nasal congestion				
Sore throat	72 (11)	58 (9)	35 (6)	43 (7)
Irritability	147 (23)	150 (24)	97 (15)	90 (14)
Headache	77 (12)	63 (10)	47 (7)	34 (5)
Chills	32 (5)	33 (5)	26 (4)	20 (3)
Vomiting	78 (12)	74 (11)	55 (9)	44 (7)
Muscle aches	34 (5)	21 (3)	16 (3)	5 (1)
Decreased	88 (14)	49 (8)	44 (7)	38 (6)
Activity				
Fever $\geq 37.5^{\circ}\text{C}$	67 (11)	61 (10)	65 (10)	66 (11)
Fever $\geq 38.5^{\circ}\text{C}$	28 (5)	24 (4)	33 (5)	37 (6)
Fever $\geq 40.0^{\circ}\text{C}$	1 (0.2)	2 (0.3)	4 (0.6)	5 (0.8)
Any reactogenic event	553 (84)	522 (81)	443 (70)	439 (70)

Groups 1 and 2 received either frozen or liquid versions of CAIV-T. The designation remains blinded at this time. The numbers in parentheses represent percentage of subjects who experienced an episode.

Good Clinical Practice and Regulatory Compliance

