CAIV-T immune response for each virus strain is measured at the end of study by an increase from baseline HAI of four-fold or greater. The primary endpoint for immunogenicity is the proportion of subjects achieving a post-vaccination serum antibody response (as defined above) for each antigen component of OPV and CAIV-T. The primary analysis interval for influenza strains A/H1N1, A/H3N2, and B is one month following the second intranasal vaccination. The primary analysis interval for poliovirus types 1, 2, and 3 is one month following the single dose of OPV.

The secondary endpoint for immunogenicity is the titre of serum antibody for each antigen component of OPV and the titre ratio to baseline of serum antibody to each virus strain of CAIV-T obtained 1 month after vaccination.

The primary analysis interval for influenza strains A/H1N1, A/H3N2, and B is one month following the second intranasal vaccination. The primary analysis interval for poliovirus types 1, 2, and 3 is one month following the single dose of OPV.

The safety objective is to assess the safety and tolerability of CAIV-T in healthy children aged 6 to less than 36 months.

The reactogenicity adverse events are:

Fever (axillary temperature > 37.5°C); Cough; Runny nose or nasal congestion; Irritability; Vomiting; Decreased activity; and Decreased appetite.

The proportion of subjects with any reactogenicity event reported and with other adverse events on any day during the 11-day period following each dose of CAIV-T or placebo will be evaluated. Serious adverse events occurring within 42 days of the first or second vaccination will be listed and summarised.

The overall incidence of reactogenicity events will be compared between the individual CAIV-T groups and the combined Placebo groups using two-sided Fisher's Exact Test. Exact 95% confidence intervals about reactogenicity adverse event frequency differences will be reported. The frequency of other adverse events will be separately compared between subjects randomised to CAIV-T or Placebo using two-sided Fisher's Exact Test.

Ethical Assurance for Protection of Human Rights

Describe in the space provided the justifications for conducting this research in human subjects. If the study needs observations on sick individuals, provide sufficient reasons for using them. Indicate how subject's rights are protected and if there is any benefit or risk to each subject of the study.

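### The reactogenicity test uses an any-event composite and a single low fever cut, and it names no comparison of co-administration with CAIV-T alone

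*Protocol*

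**What the plan says.** The safety part of the protocol's Data Analysis section fixes four things.

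- **Events.** There are seven: "Fever (axillary temperature > 37.5°C); Cough; Runny nose or nasal congestion; Irritability; Vomiting; Decreased activity; and Decreased appetite". Fever has one cut and no higher tier.
- **Summary.** "The proportion of subjects with any reactogenicity event reported and with other adverse events on any day during the 11-day period" after each dose is to be evaluated.
- **Test.** "The overall incidence of reactogenicity events will be compared" by two-sided Fisher's exact test, each CAIV-T group against pooled placebo groups (in the plural). No other group contrast is named for reactogenicity.
- **Intervals.** "Exact 95% confidence intervals about reactogenicity adverse event frequency differences will be reported". The sentence does not say whether there is one interval per listed event or one for the overall incidence.

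The group table under Research Design and Methods has three groups of 800: CAIV-T with OPV (Group 1), intranasal placebo with OPV (Group 2) and CAIV-T without OPV (Group 3). Only Group 2 receives placebo, and OPV is given only at dose 1. The third of the Specific Aims is the safety and tolerability of giving CAIV-T and OPV together. The Data Analysis section words the safety objective for CAIV-T only.

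**The concern.** The Purpose of study section says that there are no data on immune responses when the two vaccines are given together, and that no other live virus vaccine had been given within a month of CAIV-T in trials to date. The tolerability comparison is therefore new information, and it should be able to show an excess of the events that matter.

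Three features work against that.

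1. In Table 2, where every child received CAIV-T, the row "Any reactogenic event" stands at 84% and 81% after dose 1 and at 70% in both groups after dose 2. Runny nose (57-73%) and cough (42-52%) drive it. Dose 1, the only dose given with OPV, has the higher rates.
2. The single fever cut merges mild with higher fever. Table 2 itself reports 37.5, 38.5 and 40.0°C. More than half of its dose-1 fevers were below 38.5°C: 67 − 28 = 39 of 67 in one group and 61 − 24 = 37 of 61 in the other.
3. Group 1 v Group 3 is the contrast that isolates adding OPV to CAIV-T, and it is not named. Comparing CAIV-T groups with placebo answers a different question.

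The earlier CAIV-T experience under Risks and Benefits is given event by event: "the most common events were fever (5% over placebo), runny nose/nasal congestion (11% over placebo"). The planned test is coarser than that evidence.

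**Working it through.** **The plan's own power figure.** The protocol gives a power only for immunogenicity: 98% with 680 completers per group, 55% in both, a 10-point margin and one-sided 0.05. Using Φ(0.10/√(2 × 0.55 × 0.45/680) − 1.645) = Φ(3.706 − 1.645) = Φ(2.061) gives 98.0%, so it reproduces. No power is stated for safety.

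**Inputs for the safety check**
- Group size: 800 (group table; the safety population is everyone with at least one dose). The value 680 = 800 × 0.85 is used as a check.
- Baselines: midpoints of the printed Table 2 percentages after dose 1. Any event is (84 + 81)/2 = 82.5%, fever at 37.5°C is (11 + 10)/2 = 10.5%, and fever at 38.5°C is (5 + 4)/2 = 4.5%.
- Scenario: fever at or above 38.5°C doubles, from 4.5% to 9%.
- Assumption: Fisher's test is two-sided at 0.05. The protocol gives only 95% intervals.

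All Table 2 children received CAIV-T, so these baselines model Group 1 v Group 3.

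**Movement of the composite.** If fever is independent of the other symptoms, the new rate is c + (f1 − f0)(1 − c)/(1 − f0) = 0.825 + 0.045 × 0.175/0.955 = 0.833. If every extra fever falls in an otherwise event-free child, it is 0.825 + 0.045 = 0.870. If every extra fever falls in a child who already has another event, the composite does not move.

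**Movement of fever above 37.5°C.** If all extra cases are new fevers, it rises from 10.5% to 15.0%. If half are, it rises to 12.75%. If all come from children already above 37.5°C, it does not change.

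**Power of Fisher's test (simulated)**

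| Quantity tested | Rates | 800 per group | 680 per group |
|---|---|---|---|
| Any event, independent | 82.5% v 83.3% | 7% | 6% |
| Any event, no overlap | 82.5% v 87.0% | 69% | 62% |
| Fever >37.5°C, all extra cases new | 10.5% v 15.0% | 74% | 67% |
| Fever >37.5°C, half new | 10.5% v 12.75% | 26% | 22% |
| Fever >37.5°C, none new | no change | none | none |
| Fever ≥38.5°C | 4.5% v 9% | 95% | 91% |

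**Sensitivity to the baselines**
- With fever ≥38.5°C starting at 4% or 5%, power at 800 per group is 91% or 96%.
- With a composite of 80%, power is 7% (independent) or 64% (no overlap).
- After dose 2, with the composite at 70% and fever ≥38.5°C going from 5.5% to 11%, power is 11% (70% to 71.75%) or 67% (70% to 75.5%).

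The group size is adequate for this question. The choice of quantity loses the information.

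**The case against.** The strongest reply is the sentence that follows the test. It promises exact intervals in the plural, shortly after a list of seven events, and may well mean one per event. If so, part of the remedy is already planned. This stands as a reason to call the text unclear, not to call it empty. Even on that reading, the only fever rate would be at 37.5°C, with power anywhere from none to 74% in the scenario above.

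Second, by-symptom tables and fever grades are commonly left to a statistical analysis plan, which is not at hand, and daily axillary temperatures allow any cut to be derived. Agreed. But the protocol goes further than staying silent: it names the tested quantity, the fever cut and the comparator.

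Third, the 7% is not the power of the test as written, which is against placebo. That is correct. The documents give no placebo any-event rate for this symptom list, so no power for the stated contrast can be computed.

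Fourth, Table 2 comes from children aged 12-36 months, from parental worksheets without pre-defined symptoms, and from a list that adds sore throat, headache, chills and muscle aches and has no appetite item. This trial enrols from 6 months and uses staff visits with a standard questionnaire. The 81-84% is therefore indicative only. The printed percentages also differ slightly from the counts over the column heads (522/658 = 79.3% against 81% printed), which does not change the result.

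**Conclusion.** The safety comparison is weakly specified for the co-administration aim. The tested quantity is a composite that is probably near saturation after dose 1. Fever has one low cut, and the scope of the intervals is unclear. The comparator does not fit a design with one placebo group, and Group 1 v Group 3 is not named.

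For that contrast, a doubling of fever at or above 38.5°C would have about 7% power on the composite under independence, and up to about 69% with no overlap. Tested directly it would have about 95% (91-96% for baselines of 4-5%). These figures rest on Table 2 baselines, 800 per group and two-sided 0.05.

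A reader might infer that such an increase would certainly go unseen, or that about 80% of this trial's vaccinees will have an event. The documents support neither. The intervals may be per symptom, temperatures are recorded daily, the composite has moderate power in the favourable case, and the 80% comes from a differently measured population (70% after dose 2).

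**What to change.** In the safety part of Data Analysis:

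1. State that reactogenicity comparisons and exact 95% intervals are given for each of the seven listed events, after each dose.
2. Name the contrasts: Group 1 v Group 2 (adding CAIV-T to OPV) and Group 1 v Group 3 (adding OPV to CAIV-T). Align the safety objective there with the third specific aim.
3. Report fever at >37.5, ≥38.5 and ≥40.0°C from the daily axillary temperatures.
4. Keep the any-event proportion as a descriptive summary.
5. Replace the plural placebo comparator with the single placebo group, Group 2.

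The cost is wording only, with no new data or visits. The drawback is several safety comparisons in place of one, so they should be read as estimates with intervals and not as a pass/fail test. The blinding section covers only Groups 1 and 2, and Group 3 receives no oral placebo. Parent-reported symptoms in Group 1 v Group 3 therefore need more caution than measured temperature.

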This is a multi-centre study coordinated and funded by Wyeth Lederle Vaccines. Other proposed sites include Malaysia, India, Philippines, Thailand, Mexico, and Turkey. Overall 2400 participants will be entered into the study, including an estimated 350-400 from Bangladesh. The Bangladesh site will be Kamalapur an urban slum within Dhaka, where ICDDR,B operates a clinic and currently is conducting surveillance and risk factor evaluations for dengue fever and where studies on incidence of acute lower respiratory infections have been conducted.

KEY PERSONNEL (List names of all investigators including PI and their respective specialties)

Name the Project	Professional Discipline/ Specialty	Role in
1. [name]	Epidemiology	Principal Investigator

2. [name]
3. [name]
- 4.

Epidemiology
Epidemiology

Co-principal investigator
Project Manager

DESCRIPTION OF THE RESEARCH PROJECT

Concisely list in order, in the space provided, the hypothesis to be tested and the Specific Aims of the proposed study. Provide the scientific basis of the hypothesis, critically examining the observations leading to the formulation of the hypothesis.

Hypothesis to be tested: Simultaneous administration liquid trivalent cold adapted influenza vaccine and oral polio vaccine will yield antibody levels to both influenza and polio viruses that are not inferior to those produced when the vaccines are given separately.

Specific Aims:

Describe the specific aims of the proposed study. State the specific parameters, biological functions/ rates/ processes that will be assessed by specific methods (TYPE WITHIN LIMITS).

0. To demonstrate that the immune responses to the vaccine influenza viruses, as measured by serum hemagglutination inhibition assay, in children 6 to 36 months of age given influenza virus vaccine, trivalent, types A and B, live, cold-adapted (CAIV-T) concomitantly with a live, attenuated, orally-administered poliovirus vaccine (OPV), are not inferior to those immune responses in children only receiving CAIV-T.
0. To demonstrate that the immune responses to each of the three viruses contained in OPV, as measured by serum neutralisation assay, in children 6 to 36 months of age, given CAIV-T concomitantly with OPV, are not inferior to those immune responses in children only receiving OPV.
0. To assess the safety and tolerability of concomitant administration of CAIV-T with OPV.

Background of the Project including Preliminary Observations

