The study will be conducted in compliance with procedures outlined in this protocol, ICH harmonised tripartite guidelines for good clinical practice, the Declaration of Helsinki and with laws of Bangladesh.

Research Design and Methods

Describe in detail the methods and procedures that will be used to accomplish the objectives and specific aims of the project. Discuss the alternative methods that are available and justify the use of the method proposed in the study. Justify the scientific validity of the methodological approach (biomedical, social, or environmental) as an investigation tool to achieve the specific aims. Discuss the limitations and difficulties of the proposed procedures and sufficiently justify the use of them. Discuss the ethical issues related to biomedical and social research for employing special procedures, such as invasive procedures in sick children, use of isotopes or any other hazardous materials, or social questionnaires relating to individual privacy. Point out safety procedures to be observed for protection of individuals during any situations or materials that may be injurious to human health. The methodology section should be sufficiently descriptive to allow the reviewers to make valid and unambiguous assessment of the project. (DO NOT EXCEED TEN PAGES, USE CONTINUATION SHEETS).

This is a phase III, randomised, partially-blinded, placebo-controlled, multicentre outpatient study to assess the safety, tolerability and immunogenicity of Influenza Virus Vaccine, trivalent, Types A & B, Live Cold-Adapted (CAIV-T) administered concomitantly with live, attenuated, orally administered poliovirus vaccine (OPV) to 2400 healthy children aged 6 to less than 36 months. Informed consent will be sought from all parent(s)/legal guardian(s) of children before any study-related procedures are performed.

Subjects will be prospectively randomised to one of three study groups in a 1:1:1 ratio as detailed below:

Study Group	No. of Subjects	Dose 1	Dose 2
1	800	CAIV-T (IN) OPV	CAIV-T (IN)
2	800	Placebo (IN) OPV	Placebo (IN)
3	800	CAIV-T (IN)	CAIV-T (IN)

CAIV-T = influenza virus vaccine, trivalent, types A and B, live, cold-adapted;

OPV = live, attenuated, trivalent, poliovirus vaccine, administered orally;

Placebo = placebo consisting of saline only

IN = intranasal

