Designated representatives of WLW will have a masked randomisation codebreaker list of treatment assignments for vaccine administration. Holders of the codebreaker list will maintain a written log of the indications for all instances of unblinding. This log will be made available for review at study completion. Requests to unblind any given subject or subjects must be directed to WLW. The treatment will be unblinded only in the event of a medical emergency and only in cases where the unblinding is necessary for the immediate treatment of the subject.

Blinding and Vaccine Dispensing Procedures

To minimise bias in the reporting of post-vaccination reactions and other study events, neither the study subjects, their parent(s)/legal guardian(s) nor the clinical personnel will know whether intranasal CAIV-T or placebo is being administered for those subjects assigned to Study Groups 1 and 2.

All vaccines will be dispensed according to applicable local procedures, laws and regulations. Dispensing procedures will be provided to the Principal Investigator at each site and filed with all study-related documents. In addition, individuals with the responsibility of dispensing vaccines in this study will be listed on the Authorised Signature Record/Investigator Delegation Log.

Study Vaccine

Liquid CAIV-T consists of three cold-adapted influenza virus reassortants that have been concentrated and purified by centrifugation from the allantoic fluid of specific pathogen-free (SPF) chicken eggs. The formulation contains sucrose-phosphate-glutamate, acid-hydrolysed porcine gelatin and arginine as stabilisers. The total volume of 0.2 ml is administered intranasally with a spray applicator (approximately 0.1 ml into each nostril). Each dose of CAIV-T used in this study will contain approximately $10^{7+0.5}$ TCID₅₀ of each of the three influenza virus strains. The placebo consists of physiological-normal saline. The total volume of 0.2 ml is administered intranasally with a spray applicator (approximately 0.1 ml into each nostril). The concomitant vaccine will be a live, attenuated, trivalent, poliovirus vaccine (OPV). OPV will be administered orally according to the manufacturer's instructions.

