-- Administer assigned intranasal study treatment. The appropriate study personnel must update vaccine accountability records.

-- After vaccination, observe each subject for a minimum of 60 minutes. Emergency management supplies (AMBU bag, adrenaline [epinephrine], and antihistamines) will remain available for initial treatment of an allergic reaction if needed. Record any local reactions or systemic events on adverse event pages in the CRF.

-- Initiate home visits by the FRA as described above, beginning with the afternoon of the immunisation day.

-- The parent(s)/legal guardian(s) are asked to contact the FRA or field clinic immediately if any significant illness or hospitalisation occurs during the study period.

-- Any subject with a clinically significant event (e.g., high fever, convulsion, etc) should be evaluated immediately by a study physician.

-- Serious adverse events (SAEs) data, regardless of causality, will be collected up to study completion. All treatment and associated costs will be provided by the study, as described above.

-- Record all information in the appropriate source documents, and complete the CRF.

Study Visit Three, Study Termination

This visit occurs 35 (+/- 7) days after the second dose of assigned study vaccine. Surveillance staff will contact the parent/guardian and arrange for this visit to the clinic or arrange for the visit with blood collection to occur at home.

- Review subject data from the last visit.
- Obtain and record interim medical history since the last study visit (visit two). Obtain and record all adverse events and concomitant medications between Day 0 and Day 10 following second dose of assigned study treatment (see section 6.2).
- Collect approximately 5 ml of blood for immunogenicity testing.
- Serious adverse events (SAEs) data, regardless of causality, will be collected up to study completion. Any SAE ongoing at study termination must be followed until resolution.
- Record all information in the appropriate source documents, and complete the CRF.

VACCINE ADMINISTRATION

Vaccine to be Administered

At study Visit 1, each enrolled subject will receive either intranasal CAIV-T, or saline placebo, and may concomitantly receive OPV, as assigned. At Study Visit 2, the subject will receive the same intranasal study treatment that he/she received at Visit 1, but no oral treatment. The time interval between Dose 1 and Dose 2 will be 35 (+/- 7) days.

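### The safety comparisons refer to placebo groups the design does not have, mix CAIV-T with OPV at dose 1 in all but the Group 1 v Group 2 contrast, and leave out Group 1 v Group 3

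*Protocol*

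**What the plan says.** Under Research Design and Methods: "Subjects will be prospectively randomised to one of three study groups in a 1:1:1 ratio as detailed below". The table gives Group 1 CAIV-T with OPV at dose 1, Group 2 "Placebo (IN) OPV" at dose 1, and Group 3 CAIV-T without OPV, with 800 children in each. OPV is given only once. At Visit 2 "the subject will receive the same intranasal study treatment that he/she received at Visit 1, but no oral treatment".

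Under Blinding and Vaccine Dispensing Procedures, neither families nor clinical staff "will know whether intranasal CAIV-T or placebo is being administered for those subjects assigned to Study Groups 1 and 2". Group 3 is not covered, and no oral placebo is described.

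The third Specific Aim is "To assess the safety and tolerability of concomitant administration of CAIV-T with OPV". The Data Analysis section puts it differently: "The safety objective is to assess the safety and tolerability of CAIV-T in healthy children aged 6 to less than 36 months".

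Two safety comparisons follow in that section. Reactogenicity is to be "compared between the individual CAIV-T groups and the combined Placebo groups using two-sided Fisher's Exact Test", with exact 95% confidence intervals for the frequency differences. For the rest: "The frequency of other adverse events will be separately compared between subjects randomised to CAIV-T or Placebo using two-sided Fisher's Exact Test".

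**The concern.** The reactogenicity sentence uses a comparator in the plural, but only Group 2 receives intranasal placebo. An analyst must therefore reinterpret the sentence before using it. The natural repair, reading it as Group 2, exposes a second problem. Every Group 2 child has OPV at dose 1 and no Group 3 child does, so Group 3 v Group 2 is not a comparison of CAIV-T with placebo alone. The comparison of other adverse events takes no account of OPV.

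Any reaction that OPV causes would be subtracted from the apparent CAIV-T excess, so CAIV-T reactions would look rarer than they are. For a safety analysis that is the unhelpful direction. It would also occur at the dose where the protocol expects the signal: Risks and Benefits reports an excess over placebo after the first dose and no significant differences after the second.

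The third aim concerns giving the two vaccines together. One part of that question is what adding OPV does to the tolerability of CAIV-T. That is Group 1 v Group 3, a pair the plan uses for influenza immunogenicity but does not name for safety.

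**Working it through.** The protocol gives no power or precision figure for safety, so there is none to reproduce. The check is of what each contrast estimates.

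**Model at dose 1.** Let b be the background event rate, c the CAIV-T effect and d the OPV effect, assumed additive.

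- Group 1 = b + c + d
- Group 2 = b + d
- Group 3 = b + c

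**Contrasts**

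- Group 1 - Group 2 = c. OPV is balanced and both groups are blinded.
- Group 3 - Group 2 = c - d. OPV and blinding both differ.
- Mean of Groups 1 and 3, minus Group 2 = (b + c + d/2) - (b + d) = c - d/2. This applies if the comparison of other adverse events pools the two CAIV-T groups.
- Group 1 - Group 3 = d, the effect of adding OPV. It is not among the stated safety comparisons.

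**Inputs for an illustration.** c = 5 points is the fever excess after the first dose in Risks and Benefits. b = 5% is assumed. The documents do not give d, so a range is shown. Power is for a two-sided 0.05 test by normal approximation with 800 per group (1,600 v 800 when pooled); Fisher's exact test would be slightly lower.

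| Assumed d (points) | Group 1 - 2 | Group 3 - 2 | Pooled - 2 | Power, 1 v 2 | Power, 3 v 2 | Power, pooled |
|---|---|---|---|---|---|---|
| 0 | 5.0 | 5.0 | 5.0 | 97% | 97% | 99% |
| 2 | 5.0 | 3.0 | 4.0 | 93% | 58% | 89% |
| 3 | 5.0 | 2.0 | 3.5 | 90% | 29% | 77% |
| 5 | 5.0 | 0.0 | 2.5 | 86% | 5% | 43% |

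The Group 1 v Group 2 estimate does not move with d; the other two do.

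**Dose 2.** No oral treatment is given, so there is no concurrent OPV difference. What remains is that Groups 1 and 2 had OPV 35 ± 7 days earlier, and that Group 3 is not blinded.

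**Precision of the replacement contrasts**, at an assumed 30% event rate (0.3 × 0.7 = 0.21):

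- 800 v 800: 1.96 × √(0.21/800 + 0.21/800) = 4.5 points
- 1,600 v 800: 1.96 × √(0.21/1600 + 0.21/800) = 3.9 points

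**Feasibility of Group 1 v Group 3.** With 800 per group, power for a 5-point excess is about 86%, 52%, 61% and 83% at assumed base rates of 10%, 50%, 70% and 84%. For a 10-point excess it is at least 98% at each of these rates.

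**The case against.** The strongest reply is that the concomitant-use aim is already addressed. The sentence takes the CAIV-T groups individually, so Group 1 v Group 2 is planned, and it compares concomitant CAIV-T and OPV with OPV alone under blinding. This stands. A reader might infer that the plan never tests its safety aim; the documents do not support that.

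Nor would the trial be silent on adding OPV. For reactogenicity, (Group 1 - Group 2) - (Group 3 - Group 2) = Group 1 - Group 3, so a point estimate follows from planned output. Only the test and interval for that contrast are unstated. The aim is also to assess safety and carries no margin or hypothesis, and a full list of pairwise contrasts may be left to a statistical analysis plan. That weakens the omission taken alone. It does not excuse the comparator the protocol does name, which does not match its own design.

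The size of the bias is open. No OPV reaction rate is given, every child must already have had three OPV doses, and the 5-point fever excess comes from a section that summarises the frozen formulation, while this trial uses the liquid one. A reader might infer that CAIV-T reactions will be masked. The documents support only the conditional statement: masked if d is above zero.

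Two further points stand. Pooling for other adverse events is the natural reading but is not spelled out. Partial blinding is a declared design feature, and Group 1 v Group 3 shares that weakness.

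**Conclusion.** The point holds in a limited form and should be fixed. The plural comparator contradicts a design with one placebo arm. With Group 2 as comparator, Group 1 v Group 2 is valid. At dose 1, Group 3 v Group 2 estimates c - d and also compares an unblinded with a blinded group. A pooled CAIV-T v placebo comparison of other adverse events estimates c - d/2. For c = 5 and d from 0 to 5 points, the estimates run from 5 down to 0 and from 5 down to 2.5. These figures rest on additive effects and an assumed d; at d = 0 the bias from OPV vanishes. The direct OPV confounding is confined to dose 1.

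Separately, the Data Analysis section drops concomitant administration from the safety objective, and no Group 1 v Group 3 safety contrast is stated.

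**What to change.** Reword the safety part of the Data Analysis section:

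- Name Group 2 as the sole placebo arm and remove the plural comparator.
- Restate the safety objective to match the third Specific Aim, concomitant CAIV-T with OPV.
- For each dose, and for both reactogenicity and other adverse events, specify Group 1 v Group 2 (blinded CAIV-T effect on an OPV background) and Group 1 v Group 3 (effect of adding OPV, flagged as not blinded), with exact 95% confidence intervals.
- At dose 1, do not pool Groups 1 and 3 against Group 2. Report Group 3 v Group 2 as descriptive only, noting the differences in OPV and blinding.

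The cost is wording only, since the planned safety data already supply every contrast. Giving up the pooled dose 1 comparison widens the 95% half-width from about 3.9 to 4.5 points at the assumed 30% event rate. The change does not remove the open-label weakness of any contrast involving Group 3.
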